14.3 Appendix C: Hyperglycemia treatment plan

iLet Bionic Pancreas Hyperglycemia and Ketone Action Plan – for study staff

Hyperglycemia assessment:

In any time of prolonged hyperglycemia while using the iLet, always confirm with a fingerstick blood glucose reading and then:

- Ask whether the iLet is charged, reading CGM values, has insulin in the cartridge, and is dosing insulin.
 - Insulin doses can be confirmed by viewing the graph, and the algorithm steps in the history.
- Ask whether the infusion set is in place with no signs of leaking (wetness, smell of insulin, adhesive/cannula dislodged).
 - If there is ever any suspicion that the infusion set may not be working, replace it. *When in doubt, change it out!*

- Ask whether there is evidence of leaking anywhere on the fluid pathway.
 - Inspect the tubing to make sure it is patent.
 - Have the participant do the following:
 - Disconnect the tubing at the infusion site first
 - Next, remove the insulin cartridge from the chamber of the iLet.
 - Do NOT disconnect the cartridge connector from the cartridge.
 - Inspect the iLet chamber, the outside of the cartridge and the cartridge connector for signs of leaking (wetness, smell of insulin).
 - If there is no sign of leaking in the cartridge or tubing and no wetness or smell of insulin, insert the cartridge back into the iLet and twist the connector to the closed position. Then connect the tubing back to your infusion site.
 - If you suspect there might be leaking at any place in the tubing, or into the iLet itself, replace the entire cartridge and tubing set as well as the infusion set. Remember, the cartridge and tubing cannot be disconnected from each other, so a whole new cartridge with fresh insulin and new tubing must be used.
- Ask whether there is evidence of air in the tubing.
 - If there are bubbles, disconnect the tubing at the infusion site and prime the tubing until the bubbles are gone.
- Ask about recent carb intake and if a meal announcement was given.
 - If recent carb intake was not announced, was announced late, or had more carbs than originally thought, post-prandial BG will be higher and stay higher longer than if a meal announcement was correctly used. If there is no evidence of any leaking or device issues, the BG should come down on its own. Discuss best practices for meal announcements with the participant to identify any knowledge gaps and educate as needed.
- Ask about any recent disconnections or loss of CGM readings from the iLet that may have disrupted the iLet's ability to dose insulin in the past several hours.
- Ask about any other potential causes of hyperglycemia (hormonal changes, stress, etc).

Check BG if:

- Suspected infusion set failure
- CGM > 300 mg/dl for 90 minutes
- Participant is sick, vomiting or has diarrhea

Assess and document any symptoms of hyperglycemia (including but not limited to polyuria, polydipsia, nausea and vomiting). Assess and document any device issues that arise.

Ketone Action Plan: repeat testing q90 minutes until in Zone 1

Zone	Glucose	Action
1	Ketones <0.6 mmol/l	1. Assess for any potential causes of hyperglycemia. 2. If CGM is >300 90 minutes later or goes above 400 mg/dl, move to Zone 2
2	Ketones 0.6 - 2.5 mmol/l	1. Change the infusion set, even if there is no obvious leaking or sign of failure. Consider changing the cartridge and tubing if there is reason to suspect they are involved in the failure to deliver insulin.

	(Urine ketones: trace-moderate)	
If the infusion set is working and the iLet has a way to get the insulin into the participant, experience has shown that the safest way to bring down BG is to continue to wear the iLet while monitoring BG.
 
 2. Increase fluid intake. Drink 1 oz per year of age each hour for 2 hours up to 12-16 oz per hour. 3. Recheck BG and ketones every 90 minutes until ketones are < 0.6 mmol/l and BG is < 180 mg/dl. 4. If ketones remain > 0.6 mmol/l after 90 minutes, move to Zone 3
3	
Ketones > 2.5 mmol/l
 
OR
 
≥0.6 mmol/l for 90 minutes
 
(Urine ketones: large)
	
 1. Disconnect from the iLet for 2 hours. 2. Give SYRINGE/PEN injection of insulin as follows: 
 a. Help the participant navigate to the iLet Backup Therapy Screen and report what the Correction Factor says (video or picture confirmation is helpful). b. CALCULATE the correction dose: Target a glucose of 120 mg/dl by subtracting 120 mg/dl from the current blood glucose. Divide the result by the Correction Factor on the iLet Backup Therapy screen, then multiply that result by 1.25. Example (for BG of 280 mg/dl, Correction Factor of 32 mg/dl per unit): $(280 - 120) \div 32 \times 1.25$ Insulin dose = $280 \text{ mg/dl} - 120 \text{ mg/dl} = 160 \text{ mg/dl} \div 32 \text{ mg/dl per unit} = 5 \text{ units} \times 1.25 = 6.25 \text{ units}$ Round to the nearest unit. The participant will take 6 units of insulin. c. Give SYRINGE/PEN correction dose using only rapid-acting insulin. This should be whatever rapid-acting insulin the participant has available, regardless of what they were using in their iLet. 3. Instruct the participant: 
 a. Remain disconnected from the iLet for 2 hours. The iLet will still alarm for high or low CGM glucose. b. Check CGM alarm settings, and suggest they turn on the CGM Falling alarm and the Hypoglycemia alarm if they are off (in addition to the Urgent Low at 55 mg/dl). c. DO NOT reconnect to the iLet before 90 minutes after the injection because the iLet algorithms will not know about the correction injection that was taken and will stack insulin. d. DO NOT take additional correction insulin injections before allowing this injection time to work. e. AVOID high carb snacks or meals while waiting for BG to come down if possible. 
 i. Any meals/snacks with carbohydrates will require an injection of insulin to cover the carbs. Instruct the

		
participant to use the carbohydrate ratio in the iLet Backup Therapy screen to decide on a dose of injection insulin if they eat while the iLet is disconnected.
 
f. DO continue to drink fluids with no carbohydrates, continue to monitor CGM glucose, and re-check BG and ketones in 90 minutes.
 
4. Increase fluid intake. Drink 1 oz per year of age each hour for 2 hours up to 12-16 oz per hour.
 
5. RECHECK BG and ketones every 90 minutes.
 
6. 90 minutes later:
 
a. Ketones > 2.5 mmol/l (urine ketones large): Consider a second injection if BG is still elevated. Assess ability to take carbohydrates and fluids by mouth. If unable, refer to ED and follow emergency protocol procedures.b. Ketones 0.6 mmol/l to 2.5 mmol/l (urine ketones moderate or small): Reconnect to the iLet and replace the infusion set, test BG and ketones again in 90 minutes.c. Ketones < 0.6 mmol/l (urine trace or negative): Reconnect to the iLet and replace the infusion set. No further action is necessary, issue is resolved.
--	--	---

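### Appendix C, Zone 3 takes the participant off the iLet on ketones alone, but its correction dose is zero or less when BG is below 120 + 0.4 × CF

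*Combined protocol and SAP*

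**What the plan says.** All of this is in Appendix C (section 14.3) unless another section is named.

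- **Entry.** Zone 3 applies when ketones exceed 2.5 mmol/l, or have been at or above 0.6 mmol/l for 90 minutes. Zone 2 step 4 escalates on the same measure: "If ketones remain > 0.6 mmol/l after 90 minutes, move to Zone 3". Neither carries a glucose condition. Zone 2 step 3 lists ketones and glucose as separate end points: "Recheck BG and ketones every 90 minutes until ketones are < 0.6 mmol/l and BG is < 180 mg/dl".
- **Disconnection.** Zone 3 step 1 reads "Disconnect from the iLet for 2 hours", and step 3a repeats it.
- **Dose.** Step 2b says "Target a glucose of 120 mg/dl by subtracting 120 mg/dl from the current blood glucose", then divides by the CF on the iLet backup screen and multiplies by 1.25. The worked example ends "Round to the nearest unit". There is no minimum dose, no glucose floor and no instruction for a zero or negative result.
- **Reason for staying off.** Step 3c: "DO NOT reconnect to the iLet before 90 minutes after the injection because the iLet algorithms will not know about the correction injection".
- **After 90 minutes.** Step 6a (ketones above 2.5) says "Consider a second injection if BG is still elevated. Assess ability to take carbohydrates and fluids by mouth. If unable, refer to ED". Step 6b (ketones 0.6 to 2.5) says "Reconnect to the iLet and replace the infusion set, test BG and ketones again in 90 minutes". Step 6c (below 0.6) also reconnects.
- **Other sections.** Section 7.2 has participants on injections stop all insulin not delivered by the device once the iLet starts. Section 7.7.7 requires anyone in Zone 3 to speak directly to a clinician and the site PI to be informed.

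**The concern.** Zone 3 is the plan's rescue step when ketones persist after a set change. It trades the iLet's delivery for an injection, and that trade makes sense only if there is an injection. The trigger is ketones while the dose depends on glucose, so the two can part. A participant with persistent ketones and glucose near target meets the trigger, comes off the device, and is given a calculated correction dose of zero. The written rule then delivers less insulin than leaving the iLet on, which is the opposite of its purpose. What is at stake is participant safety in a rare situation. Neither the primary outcome nor any efficacy analysis depends on it.

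**Working it through.** **Inputs.** Target 120 mg/dl, multiplier 1.25, rounding to the nearest unit, and the example values BG 280 mg/dl and CF 32 mg/dl per unit all come from Zone 3 step 2b. CF 32 is the only CF in the documents; every other CF below is assumed.

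**Reproducing the plan's example.** (280 − 120)/32 × 1.25 = 6.25, which rounds to 6 units. This matches.

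**Where the dose vanishes.** The rounded dose is 0 or less when (BG − 120)/CF × 1.25 < 0.5, that is, when BG < 120 + 0.5 × CF/1.25 = 120 + 0.4 × CF.

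| CF (mg/dl per unit) | Boundary (mg/dl) |
|---|---|
| 20 (assumed) | 128 |
| 32 (stated) | 132.8 |
| 50 (assumed) | 140 |
| 75 (assumed) | 150 |
| 100 (assumed) | 160 |

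At CF 32:

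- BG 133 gives 0.51, rounded to 1 unit.
- BG 130 gives 0.39, rounded to 0.
- BG 125 gives 0.20, rounded to 0.
- BG 110 gives −0.39, which also rounds to 0.

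Between 120 and the boundary the raw dose is positive but rounds away; only below 120 is it negative.

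**Time without correction insulin.** Steps 6b and 6c allow reconnection at 90 minutes; steps 1 and 3a say 2 hours. The gap is therefore 90 minutes to 2 hours.

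**Can the case arise?** The text allows it in two ways.

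1. Section 7.7.4 requires a ketone check for symptoms of ketoacidosis, with no glucose threshold.
2. After the Zone 2 set change, glucose may fall faster than ketones, and step 4 then escalates on ketones alone. This route is narrow. From 300 mg/dl, the level that (after 90 minutes) prompts a ketone check, glucose must fall (300 − 132.8)/90 = 1.86 mg/dl per minute at CF 32, or (300 − 160)/90 = 1.56 at CF 100. From an assumed 250 mg/dl the rates are (250 − 132.8)/90 = 1.30 and (250 − 160)/90 = 1.00. For scale, section 7.7.2 treats changes above 2 mg/dl per minute as steep.

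Two other routes are not relied on. Illness prompts a glucose check in Appendix C, not a ketone check. The retest after step 6b might lead back to Zone 3, but staff could equally read it as Zone 2.

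**Does the reason for disconnection survive a zero dose?** Step 3c explains the wait by an injection the algorithm cannot see. With no injection there is nothing to stack. Zone 2 step 1 also tells staff that, if the set works, continuing on the iLet while monitoring is the safest way to lower glucose.

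**The case against.** The strongest reply is that this is a hyperglycemia plan. Its introduction speaks of prolonged hyperglycemia confirmed by fingerstick, and Zone 3 talks of waiting for glucose to come down. A correction formula that returns zero near target is doing its job. A participant whose glucose has dropped that fast after a set change is probably receiving insulin, with more still acting (section 1.2 gives clearance of 4 to 8 hours). Ketoacidosis is described as very rare in CFRD because of residual beta-cell function (section 7.7.4). The insulin-sensitive participants for whom the boundary is highest are also, on section 1.3's reasoning, likely to have such function. All of this stands, and it keeps the point small. It does not supply the missing rule: section 7.7.7 says who must be spoken to, not what to do when the formula gives zero, and that clinician is working from this sheet.

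A reader might infer more than the documents support:

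- **That nothing in the plan covers such a participant.** Steps 3e to 6 still apply: injected insulin for carbohydrate, fluids, rechecks, reconnection, and under step 6a the oral-intake check with emergency referral. What is missing is narrower: a rule for a zero or negative dose.
- **That Zone 3 breaks the 1-hour removal limit in section 7.7.2.** That limit governs removal by the participant, for example for bathing. Zone 3 is directed by staff and lasts as long for those who do get an injection, so the limit does not measure this gap.
- **That Zone 3 contradicts section 7.7.2, which answers raised ketones with a set change and device dosing.** That instruction corresponds to Zone 2; Zone 3 is the escalation when it fails.
- **That step 6a must be rewritten too.** How to manage ketones above 2.5 mmol/l with glucose not elevated is a clinical judgement the documents do not settle.

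**Conclusion.** The point holds as a minor safety correction. Zone 3 disconnects on ketones without regard to glucose, and its correction dose is zero or less below 120 + 0.4 × CF. Followed literally, a participant in that range has no basal delivery for 90 minutes to 2 hours and no correction insulin, although the plan's stated reason for staying off is absent. The boundary of 132.8 mg/dl rests on the plan's own CF of 32; the range of 128 to 160 mg/dl rests on an assumed CF of 20 to 100. The case is uncommon, and the documents allow no estimate of how often it would occur. They do not support a claim that harm is likely: insulin on board, residual secretion, rechecks and clinician contact all limit it. Efficacy results are unaffected.

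**What to change.** Make Zone 3 steps 1 and 3a conditional on an injection being given, and add to step 2b: *If the calculated dose rounds to 0 or less, do not disconnect; replace the infusion set (and the cartridge and tubing if delivery is in doubt), stay on the iLet, consult the on-call MD or NP, and recheck BG and ketones in 90 minutes; disconnect only if injected insulin is ordered.*

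Step 3c's protection against stacking is kept, because no injection is given while the participant is connected. Section 7.7.7 already has an MD or NP on call at all times.

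The cost is a short wording change and a staff retraining note, with no new visits, procedures or participants. There is one limitation: near its 120 mg/dl target the iLet may give little more than basal insulin, and a set change has not yet cleared the ketones. That is why the new line calls for the MD or NP and does not rely on the device alone.

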7.7.2 Bionic Pancreas Study Arm

- Participants will keep their bionic pancreas charged, which will require charging with the study provided charger at least once per day.
- Participants will keep their study issued Precision Xtra ketone meter, extra infusion sets and insulin vials and syringes or insulin pens easily accessible at all times.
 - Participants will be required to check their ketone levels whenever their CGM has been above 300 mg/dl for 90 minutes and to notify study staff if the result is ≥ 0.6 mmol/l.

- During the experiment, the iLet bionic pancreas will be worn by the participant at all times to ensure good radio-frequency signal reception.
 - The bionic pancreas is not waterproof and therefore must be removed for water activities, including showering. Participants are urged to take appropriate precautions when they are disconnected from the bionic pancreas, including frequent BG checks and having carbohydrate readily available.
 - The Dexcom CGM transmitter is water resistant and can be left on for bathing and swimming.
 - Participants may not remove the iLet bionic pancreas for more than 1 hour at a time (e.g. for bathing) and may not remove it for more than 2 hours total in any 24-hour period.
- Participants will be asked to change their infusion set and cartridge every 3 days.
 - Participants will be taught to replace their infusion set if there is any doubt that it may not be working. They will be taught how to recognize potential infusion site failures.
 - Participants will be taught to replace their infusion set if their ketones are ≥ 0.6 mmol/l. More details pertaining to hyperglycemia management can be found in Appendix C.
- Participants will receive alerts if Dexcom CGM Bluetooth connection is interrupted for more than 2 hours.
 - If a Dexcom CGM sensor fails during the course of an experiment, the iLet will provide basal insulin based on past requirements and will allow announcement of meals and entry of fingerstick BG measurements, which will be treated by the algorithm in the same way as Dexcom CGM data and may result in administration of insulin or temporary suspension of insulin delivery. The Dexcom CGM sensor will be replaced as soon as possible and normal bionic pancreas control will resume when the new sensor is online.

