- If the BG measurement is consistent with a low glucose: the participant will treat hypoglycemia with carbohydrates. Participants will be instructed to consider using less carbohydrate to treat or prevent hypoglycemia, since due to insulin suspension 5-10 grams is often sufficient and is less likely to lead to hyperglycemia.
- Participants will be trained on troubleshooting for various scenarios that could lead to hyperglycemia. For instance, hyperglycemia could be due to true hyperglycemia or poor Dexcom CGM calibration.
 - The first step in responding to hyperglycemia according to the CGM will be to perform fingerstick BG and ketone measurements.
 - If the BG measurement is not consistent with the CGM glucose: the participant will calibrate the Dexcom CGM as long as there has been no carbohydrate intake in the last 30 minutes and there is no steep rise or fall in glucose (>2 mg/dl/min). If a calibration is delayed for this reason, it will be performed at the next opportunity if it is still necessary. The participant will be taught to continue to monitor CGM and BG measurements to confirm accuracy and normoglycemia.
 - If the BG measurement is consistent with the CGM glucose:
 - Participants will be asked to investigate their insulin infusion set and consider replacing it, check for any occlusions along the fluid path, and check to make sure that the cartridge is not empty.
 - Study staff will recommend the participant continue to monitor their BG until it returns to normoglycemia, and to contact study staff with any questions or concerns.
 - If ketones ≥ 0.6 mmol/L are present:
 - Participants will be advised to change their pump infusion set and will be reminded that the BP should dose insulin accordingly.
 - Study staff will recommend the participant continue to monitor their ketone levels and BG every 60 minutes until ketones return to < 0.6 mmol/L and BG is < 180 mg/dl, and to contact study staff with any questions.
 - If participants experience persistent hyperglycemia lasting more than 2 hours, they will be instructed to contact study staff for consideration of infusion set replacement and/or correction insulin according to the above protocol.

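### Appendix C, Zone 3 step 6c closes a ketone episode on ketones alone, while section 7.7.2 and Zone 2 step 3 also require glucose below 180 mg/dl; the recheck intervals differ too

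*Combined protocol and SAP*

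**What the plan says.** Appendix C is headed "iLet Bionic Pancreas Hyperglycemia and Ketone Action Plan – for study staff", and section 7.7.2 points to it: "More details pertaining to hyperglycemia management can be found in Appendix C". Neither place says which text governs if they differ.

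- **Zone 3 step 6c** (90 minutes after the correction injection, ketones below 0.6 mmol/l): "Reconnect to the iLet and replace the infusion set. No further action is necessary, issue is resolved". Glucose is not mentioned.
- **Section 7.7.2**, for a participant with ketones of 0.6 mmol/l or more: "Study staff will recommend the participant continue to monitor their ketone levels and BG every 60 minutes until ketones return to < 0.6 mmol/L". The sentence then adds a glucose condition, so the end point is "until ketones return to < 0.6 mmol/L and BG is < 180 mg/dl".
- **Zone 2 step 3**: "Recheck BG and ketones every 90 minutes until ketones are < 0.6 mmol/l and BG is < 180 mg/dl".
- **Table heading in Appendix C**: "Ketone Action Plan: repeat testing q90 minutes until in Zone 1". Zone 1 is defined by ketones below 0.6 mmol/l alone.

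Zone 3 is also unclear about time off the device. Steps 1 and 3a ask for 2 hours of disconnection. Step 3c forbids reconnection only before 90 minutes, and steps 6b and 6c reconnect at the 90-minute check.

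**The concern.** Zone 3 is for ketones above 2.5 mmol/l, or ketones that have stayed at 0.6 mmol/l or more for 90 minutes. These participants have come off the iLet, taken a manual insulin injection, and are about to resume automated delivery through a newly placed infusion set. A set that fails at that point would show first as glucose that does not fall. Step 6c tells staff the matter is closed at that moment, whatever the glucose.

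Staff working from the appendix would stop the paired glucose and ketone checks sooner than the protocol body recommends. Staff working from 7.7.2 would continue, at a different interval. What is at stake is consistent safety follow-up in a small group, not the efficacy analysis.

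**Working it through.** The plan gives no figure to reproduce on the closing rule, so the check is a comparison of the texts.

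| Place | Recheck interval | Checks end when |
|---|---|---|
| 7.7.2, ketones 0.6 or more | 60 min | ketones <0.6 and glucose <180 |
| Appendix C, Zone 2 step 3 | 90 min | ketones <0.6 and glucose <180 |
| Appendix C, table heading | 90 min | Zone 1 (ketones <0.6) |
| Appendix C, Zone 3 steps 5 and 6c | 90 min | ketones <0.6 |

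**Interval.** Over 3 hours, 7.7.2 gives 180/60 = 3 checks and Appendix C gives 180/90 = 2.

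**A traced case.** Take a Zone 3 participant with ketones 0.5 mmol/l and glucose 220 mg/dl at the 90-minute check.

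1. Step 6c: 0.5 < 0.6, so resolved.
2. Section 7.7.2: 0.5 < 0.6 is met, but 220 is not below 180, so checks continue.
3. Zone 1 step 2 (CGM above 300 mg/dl 90 minutes later, or above 400, moves to Zone 2): not triggered.
4. iLet high alarm (300 mg/dl or more for 90 minutes): silent.
5. Section 7.7.4 ketone triggers (above 300 for 90 minutes, above 400 once, or symptoms of ketoacidosis): not triggered by the glucose value.
6. Section 7.7.2 general rules: glucose monitoring to normoglycemia is recommended, and hyperglycemia beyond 2 hours prompts contact with staff. Participants are also trained to measure glucose and ketones as a first response to high CGM values, but no level or repeat interval is given.

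If glucose instead stays above 300 mg/dl, items 3 to 5 come into play. The uncovered band is therefore mainly 180 to about 300 mg/dl.

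**Cost of closing the gap.** The documents give no glucose course after the injection, so this is a rough bound under assumptions. The plan's dosing example is (280 − 120)/32 × 1.25 = 6.25 units, rounded: "Round to the nearest unit. The participant will take 6 units of insulin". Assume that the share of the dose absorbed by t minutes is F(t) = 1 − (1 + t/m)·exp(−t/m), with m the peak time. Take m as 65 minutes (the iLet default, assumed to hold for the injection) or 90 minutes (the top of the range in section 1.2). Take the effect per unit as 32 mg/dl, or 32/1.25 = 25.6 mg/dl. Glucose reaches 180 when dose × effect × F(t) = starting glucose − 180.

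| Start | Dose | Effect | m | F needed | Minutes to 180 | Extra checks, 60 / 90 min |
|---|---|---|---|---|---|---|
| 280 | 6 | 32 | 65 | 100/192 = 0.521 | 113 | 1 / 1 |
| 280 | 6 | 25.6 | 90 | 100/153.6 = 0.651 | 200 | 2 / 2 |
| 310 | 7 | 25.6 | 90 | 130/179.2 = 0.725 | 231 | 3 / 2 |
| 400 | 11 | 25.6 | 90 | 220/281.6 = 0.781 | 259 | 3 / 2 |

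Extra checks are (minutes − 90)/interval, rounded up. In the last row these are 169/60 = 2.8, so 3, and 169/90 = 1.9, so 2. The starting values of 310 and 400 are assumed. The curve ignores iLet dosing after reconnection, residual beta-cell function and food. It has no ketone term, so it says nothing about how often ketones clear while glucose stays at 180 mg/dl or above. It is used only to size the added checks.

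**The case against.** The best defence is that the two texts describe different stages. The 7.7.2 bullet has the participant change the set and rely on the iLet to dose, which matches Zone 2, and there the end points agree. Zone 3 is a later escalation, and Appendix C could be read as the specific rule for it. That reading is reasonable. However, the 7.7.2 trigger has no upper ketone limit, nothing states that the appendix takes over, and the intervals differ even at the matching stage.

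Other points on that side stand in full. Staff who keep checking breach neither text, and 7.7.2 is worded as a recommendation. A participant at step 6c meets the Zone 1 definition, so the Zone 1 glucose rule is available on the same sheet. Appendix C also regards staying on a working iLet while glucose is monitored as the safest way to bring glucose down.

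A reader might infer three stronger things that the documents do not support:

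- That Zones 2 and 3 contradict each other directly. They are inconsistent, but Zone 2 step 3 does not govern someone leaving Zone 3 with ketones below 0.6 mmol/l.
- That participants are left without any safeguard. The rules traced above show otherwise.
- That glucose of 180 mg/dl or more at 90 minutes means the treatment has failed. Part of a working dose may still be unabsorbed by then.

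**Conclusion.** The inconsistency is real and worth correcting. Step 6c ends follow-up on ketones alone, whereas 7.7.2 and Zone 2 step 3 require glucose below 180 mg/dl as well, and the intervals are 60 and 90 minutes. Confidence in the wording is high.

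The consequence is limited. It concerns mainly glucose of 180 to about 300 mg/dl with ketones cleared, in someone returning to automated dosing. The documents give no rate of reaching step 6c and no joint frequency of cleared ketones with raised glucose. They describe ketoacidosis as very rare in CFRD, so few participants are likely to be affected; that is a judgement, not an estimate. The primary analysis and the sample size do not depend on this rule.

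**What to change.** 1. Reword step 6c along these lines: *Ketones <0.6 mmol/l: replace the infusion set and reconnect to the iLet once the required disconnection time has passed. If BG is <180 mg/dl, resolved. If BG is ≥180 mg/dl, recheck BG and ketones every 90 minutes until ketones are <0.6 mmol/l and BG is <180 mg/dl.*
2. Change the interval in 7.7.2 from 60 to 90 minutes. This needs the fewest edits, because Appendix C uses 90 minutes throughout.
3. State one disconnection time in Zone 3, and make steps 1, 3a, 3c and 6 agree with it.
4. If the table heading is also edited, limit the joint criterion to participants who have had ketones of 0.6 mmol/l or more, so that those only ever in Zone 1 get no added testing.

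No new threshold is introduced. The cost is a few lines of text, an updated staff training sheet, and roughly one to three extra fingerstick glucose and ketone checks per affected episode. In the cases worked above it is one or two at the 90-minute interval; three arises only at 60 minutes.
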